Research Protocol

Effect of Different Inspired Oxygen Concentrations on Intraoperative Lung Recruitment Efficacy in Patients Undergoing Abdominal Surgery

Sponsoring Institution: Northern Jiangsu People's Hospital

Leading Institution: NA

Responsible Department: Department of Anesthesiology

Principal Investigator: [name]

Study Period: December 2024 to February 2026

Version Number: V1.0

Version Date: October 16, 2024

Table of Contents

1. Protocol Summary 3
2. Research Background 4
3. Research Objectives 6
4. Study Design, Principles, and Procedures 6
 - 4.1 Study Design 6
 - 4.2 Study Procedures 6
 - 4.3 Indications 6
 - 4.4 Study Endpoints 7
5. Study Subjects 7
 - 5.1 Study Population 7
 - 5.2 Inclusion Criteria 7
 - 5.3 Exclusion Criteria 7
 - 5.4 Exclusion Criteria 7
 - 5.5 Recruitment Process 8
 - 5.6 Criteria for Terminating the Study 8
6. Research Methods and Technical Route 8
 - 6.1 Study Grouping 8
 - 6.2 Intervention Measures 8
 - 6.3 Study Intervention Protocol 8
 - 6.4 Concomitant Medications 9

6.5 Study Flowchart 9

6.6 Study-Related Laboratory Tests 9

6.7 Study-Related Imaging Examinations 10

7. Efficacy Evaluation Criteria 10

8. Observation Items and Detection Time Points 10

9. Observation of Adverse Events 10

9.1 Definition and Assessment of Adverse Events 10

9.2 Recording and Handling of Adverse Events 10

9.2.1 Recording of Adverse Events 10

9.2.2 Handling of Adverse Events 11

9.2.3 Reporting of Adverse Events 11

10. Quality Control and Quality Assurance 11

11. Data Safety Monitoring 11

12. Statistical Analysis 12

12.1 Statistical Methods (Including Description of Statistical Methods, Statistical Software and Version) 12

12.2 Sample Size Calculation Process 12

13. Ethics of Clinical Research 12

14. Collection and Storage of Samples/Specimens 13

15. Study Progress 13

16. References 14

1. Protocol Summary

Item	Details
Project Name	Effect of Different Inspired Oxygen Concentrations on Intraoperative Lung Recruitment Efficacy in Patients Undergoing Abdominal Surgery
Research Objective	To investigate the effect of different inspired oxygen concentrations on intraoperative lung recruitment efficacy in patients undergoing abdominal surgery
Study Design	A single-center, prospective, randomized controlled study Study population: Patients undergoing elective abdominal surgery Trial protocol: Primary outcome measure: Time to recovery of lung compliance; Secondary

	
outcome measures: Comparison of oxygenation index before anesthesia induction and after extubation, degree of atelectasis at the end of surgery, incidence of hypoxemia during PACU stay, and incidence of pulmonary complications within 3 days after surgery.
																																																																										
Sample Size	
88 cases
 
Sample size calculation process Based on preliminary experimental results, sample size was calculated using PASS, with a 20% dropout rate, resulting in a total sample size of 88 cases (22 cases in each group).
 
Input:
 
Power and Alpha
 
Power 0.95
 
Alpha 0.05
 
Group 4
 
Group Allocation Equal
 
Effect size
 
Means 30 34 50 53
 
K 1
 
σ 7 6 15 19
 
Numeric Results Means: 30 34 50 53
 
  
 Power	Average	n	G	Total	K	Std Dev of Means	Standard Deviation	Effect Size	Alpha	
   
 0.9707	3.00	4	4	12	1.00	9.91	6.00	1.6515	0.0500	
 
 0.9875	4.00	4	4	16	1.00	9.91	7.00	1.4156	0.0500	
 
 0.9526	11.00	4	4	44	1.00	9.91	15.00	0.6606	0.0500	
 
 0.9526	17.00	4	4	68	1.00	9.91	19.00	0.5215	0.0500	
  
 
One-Way Analysis of Variance F-Tests
 
Dropout-Inflated Sample Size (Continued)
 
  
 Average	Group	Sample Size	n	Group	Dropout Rate	Sample Size	Ni	Dropout-Inflated Enrollment Sample Size	Ni'	Expected Number of Dropouts	Di	
   
 17.00	1 - 4	Total	17	1 - 4	20%	68	17	22	88	5	20	
  
	Power	Average	n	G	Total	K	Std Dev of Means	Standard Deviation	Effect Size	Alpha	0.9707	3.00	4	4	12	1.00	9.91	6.00	1.6515	0.0500	0.9875	4.00	4	4	16	1.00	9.91	7.00	1.4156	0.0500	0.9526	11.00	4	4	44	1.00	9.91	15.00	0.6606	0.0500	0.9526	17.00	4	4	68	1.00	9.91	19.00	0.5215	0.0500	Average	Group	Sample Size	n	Group	Dropout Rate	Sample Size	Ni	Dropout-Inflated Enrollment Sample Size	Ni'	Expected Number of Dropouts	Di	17.00	1 - 4	Total	17	1 - 4	20%	68	17	22	88	5	20
Power	Average	n	G	Total	K	Std Dev of Means	Standard Deviation	Effect Size	Alpha																																																																		
0.9707	3.00	4	4	12	1.00	9.91	6.00	1.6515	0.0500																																																																		
0.9875	4.00	4	4	16	1.00	9.91	7.00	1.4156	0.0500																																																																		
0.9526	11.00	4	4	44	1.00	9.91	15.00	0.6606	0.0500																																																																		
0.9526	17.00	4	4	68	1.00	9.91	19.00	0.5215	0.0500																																																																		
Average	Group	Sample Size	n	Group	Dropout Rate	Sample Size	Ni	Dropout-Inflated Enrollment Sample Size	Ni'	Expected Number of Dropouts	Di																																																																
17.00	1 - 4	Total	17	1 - 4	20%	68	17	22	88	5	20																																																																
Case Selection	
Target population: Patients undergoing abdominal surgery
																																																																										
	
Inclusion Criteria
 
Patients with ASA physical status I - II;Patients who voluntarily participate in the study and sign the informed consent form;Patients undergoing elective abdominal surgery under general anesthesia;Gender 不限, aged 18-64 years, BMI 18-25 kg/m²;Expected operation time ≥1.5 hours, and intraoperative blood loss ≤500 ml.
																																																																										

	Exclusion CriteriaPrevious thoracic surgery; chest X-ray or CT indicating pneumothorax or pulmonary bullae;Pulmonary diseases: chronic bronchitis, asthma, moderate to severe obstructive ventilatory dysfunction; preoperative pulse oxygen saturation (SpO_2) <90% in room air or <95% with oxygen inhalation; contraindications to lung recruitment: high intracranial pressure, hypovolemic shock, right heart failure;Severe heart disease (New York Heart Association, NYHA class III or IV; acute coronary syndrome or persistent ventricular tachyarrhythmia);Participation in other interventional studies or refusal to enroll.
Treatment Protocol	None
Efficacy Evaluation	Efficacy evaluation indicators (primary and secondary efficacy indicators)Primary outcome indicator: Time for dynamic lung compliance (C_{dyn}) to return to baseline after lung recruitment;Secondary outcome indicators: Degree of atelectasis immediately after extubation, evaluated by lung ultrasound; oxygenation index at T0-T5; incidence of hypoxemia and duration of oxygen therapy during PACU stay; pulmonary complications within 3 days after surgery, evaluated by postoperative chest X-ray or CT, with atelectasis assessed by lung ultrasound.
	Safety evaluation indicators: None
Statistical Methods	Descriptive statistics, Mann-Whitney U test, t-test, Chi-square test, etc.

2. Research Background

During perioperative mechanical ventilation, high fractional inspired oxygen (FiO_2) is usually administered to prevent hypoxemia. Although numerous studies have shown that the use of high FiO_2 during surgery can improve oxygen supply to vital organs such as the heart, brain, and kidneys, inhalation of high-concentration oxygen is also a risk factor for postoperative pulmonary complications. Therefore, there is no consensus on the optimal intraoperative FiO_2 setting[1].

Lung recruitment typically includes manual lung recruitment and ventilator-driven lung recruitment, with the latter including vital capacity maneuver, pressure-controlled method, and volume-controlled method. Various lung recruitment methods can effectively open alveoli and improve oxygenation[3].

Evaluation of lung recruitment efficacy includes pressure-volume (P-V) curve, electrical impedance tomography (EIT), and lung ultrasound (LUS).

The P-V curve describes the relationship between airway pressure and tidal volume, reflecting the mechanical properties of the lungs and chest wall, and can assist in judging the

ventilation status of the lungs. A normal P-V curve is "S"-shaped, with the zero point representing functional residual capacity (FRC), and the volume change range being tidal volume. The P-V curve is an effective bedside tool for evaluating respiratory mechanics and lung recruitment efficacy.

The basic principle of EIT is to apply weak voltage and current to the human body through local electrodes, sense changes in internal bioelectrical impedance, and reconstruct internal structure images using algorithms. High extracellular fluid content, high electrolyte concentration, large cell volume, and multiple intercellular connections reduce impedance, while adipose tissue, bone, and air increase impedance. This method is non-invasive, simple, and provides rich information, and can be used for bedside detection and monitoring. Gas has high impedance, and blood flow has low impedance; thoracic impedance changes with ventilation and blood flow. Moreover, lung tissue is close to the body surface, so changes in lung volume and conductivity can be easily detected. In animal models, indicators such as ventilation center shift, compliance of dependent and non-dependent lung regions, and tidal distribution index on EIT can assist in judging changes in local ventilation distribution during lung recruitment[4]. Spadaro et al. dynamically monitored the ventilation status of the gravity-dependent static lung zone (DSS) using EIT and evaluated lung recruitment efficacy using the P-V curve. During lung recruitment, with the increase of PEEP, DSS decreased while lung recruitment volume increased. The opposite change occurred when PEEP decreased. DSS was correlated with changes in lung recruitment volume ($r=0.734$, $P<0.001$). EIT can calculate the compliance of local lung regions to judge the impact of PEEP on local alveolar ventilation and can also be used for titrating individualized PEEP.

Although computed tomography (CT) is considered the "gold standard" for evaluating lung recruitment efficacy, its high requirements for equipment and site, as well as large radiation dose, limit its use. LUS can also be used to check the ventilation status of the lungs, because diseases change the ratio of gas to fluid in the lungs, and LUS shows corresponding signs such as tissue-like changes and "fragment sign". Quantitative evaluation can also be performed using LUS scores. Song et al.[5] used ultrasound-guided lung recruitment in children under 1 year old, which significantly reduced the incidence of atelectasis. Wu et al.[6] compared the effects of ultrasound-guided lung recruitment, manual lung recruitment, and mechanical ventilation without lung recruitment in laparoscopic gynecological surgery, and the results showed that lung recruitment improved intraoperative oxygenation and reduced LUS scores, with the ultrasound-guided group having the best effect. Even 30 minutes after tracheal extubation, the difference in LUS scores between groups remained significant. However, no differences were observed in PPC, postoperative pain, or postoperative hospital stay, which may be related to normal preoperative lung function and short operation time in all patients.

Most current studies tend to inhale low-concentration oxygen while ensuring adequate oxygenation. Studies have shown that inhalation of high-concentration oxygen during surgery and before extubation can lead to postoperative atelectasis and even impair postoperative oxygenation function. However, blindly reducing FiO₂ before extubation may bring troubles to crisis management after extubation, and it is not beneficial to blindly reduce FiO₂ without ensuring adequate airway patency[7]. Studies have shown that applying 10 cmH₂O continuous positive airway pressure before and during induction, and 10 cmH₂O

PEEP during surgery can improve oxygenation function in patients undergoing laparoscopic surgery. This seems to suggest that if high-concentration oxygen is inhaled during surgery, alveolar patency can be maintained by applying continuous positive airway pressure, and then FiO₂ can be gradually reduced to reduce the risk of postoperative atelectasis and hypoxemia.

Dynamic lung compliance can monitor alveolar changes in real-time, which is of great significance for evaluating intraoperative lung function. The value of compliance represents the number of gas-containing alveoli; the more alveoli collapse, the less gas-containing tissue, and the lower the compliance, which can objectively reflect lung function. With the continuous development of medical technology, laparoscopic surgery has become increasingly popular. Studies have found that intraoperative pneumoperitoneum can increase intra-abdominal pressure, cause diaphragmatic elevation, significantly reduce end-expiratory lung volume, and abnormal distribution of ventilation/perfusion ratio. In gynecological laparoscopic surgery, patients usually adopt the Trendelenburg position. Under the influence of gravity, the Trendelenburg position further exacerbates the compression of the diaphragm, leading to alveolar collapse, further reduction of functional residual capacity and dynamic lung compliance, and increased risk of postoperative atelectasis[2].

As part of the lung-protective ventilation strategy, lung recruitment has been widely used. However, there is no unified consensus on lung recruitment strategies in current international guidelines. The time for lung compliance to return to baseline after lung recruitment is unclear, and the optimal inspired oxygen concentration that can benefit patients from lung recruitment is uncertain. Based on this, this study intends to evaluate the effect of different inspired oxygen concentrations on lung recruitment efficacy in patients undergoing abdominal surgery.

3. Research Objectives

3.1 Primary objective: To investigate the effect of different inspired oxygen concentrations on the time for lung compliance to return to baseline after lung recruitment in patients undergoing abdominal surgery;

3.2 Secondary objectives: To explore the comparison of oxygenation index before anesthesia induction and after extubation, incidence of hypoxemia during PACU stay, incidence of atelectasis after extubation, and incidence of pulmonary complications within 3 days after surgery in patients undergoing abdominal surgery with different inspired oxygen concentrations after lung recruitment;

4. Study Design, Principles, and Procedures

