6.7 Study-Related Imaging Examinations

Electrocardiogram

7. Efficacy Evaluation Criteria

Observation of primary outcome indicators: Time for dynamic lung compliance (Cdyn) to return to baseline after lung recruitment. Respiratory mechanics parameters and hemodynamic parameters at T1-T5 were recorded, including Cdyn, PIP, Ppeak, Pplat, Vt, PEEP, MP, Pdrive, BP, HR;

Observation of secondary outcome indicators: Degree of atelectasis immediately after extubation, evaluated by lung ultrasound; oxygenation index at T0-T5; incidence of hypoxemia and duration of oxygen therapy during PACU stay; pulmonary complications within 3 days after surgery, evaluated by postoperative chest X-ray or CT, with atelectasis assessed by lung ultrasound.

8. Observation Items and Detection Time Points

Before the first lung recruitment (RM1) after surgery starts (T1), immediately after RM1 (T2), before RM2 (T3), immediately after RM2 (T4), and immediately at the end of surgery (T5). Primary and secondary outcome indicators were observed. Degree of atelectasis immediately after extubation, evaluated by lung ultrasound; oxygenation index at T0-T5; incidence of hypoxemia and duration of oxygen therapy during PACU stay; pulmonary complications within 3 days after surgery, evaluated by postoperative chest X-ray or CT, with atelectasis assessed by lung ultrasound.

9. Observation of Adverse Events

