12.1 Statistical Methods

All data were statistically analyzed using SPSS 26.0 software, with $P<0.05$ indicating a statistically significant difference. Count data were expressed as cases or percentages and analyzed using the Chi-square test or Fisher's exact test. Normality of measurement data was evaluated using the Kolmogorov-Smirnov test or Shapiro-Wilk test. Measurement data conforming to a normal distribution were expressed as mean \pm standard deviation ($x\pm s$) and analyzed using the t-test; count data with repeated measurements were analyzed using one-way ANOVA; skewed or unknown-distribution measurement data were expressed as median (interquartile range) [median (IQR)] and analyzed using the Mann-Whitney U test.

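### The before/after oxygenation index outcome has only unadjusted tests; a four-arm ANCOVA on the pre-induction value would be clearer and probably more precise

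*Protocol*

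**What the plan says.** The oxygenation index appears in two forms.

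- **Two time points.** The Protocol Summary gives the secondary outcome as "Comparison of oxygenation index before anesthesia induction and after extubation". Objective 3.2 opens with the same contrast, "To explore the comparison of oxygenation index before anesthesia induction and after extubation", and ends by tying it to patients "with different inspired oxygen concentrations after lung recruitment".
- **A series.** The efficacy evaluation row of the Summary, section 7 and section 8 give "oxygenation index at T0-T5". Section 8 defines T1 to T5, from before the first recruitment manoeuvre to the end of surgery. It does not define T0, and no listed time falls after extubation.

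Section 12.1 assigns tests by type of data. Normally distributed measurements are summarised by mean and SD "and analyzed using the t-test"; skewed ones go to the Mann-Whitney U test. One-way ANOVA is named for repeated measurements, although the sentence calls these count data. No method with a baseline covariate is listed.

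Sections 4.2, 6.1 and 6.3 set the assigned FiO2 only after surgery has started.

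**The concern.** The label names a contrast between two times, and the listed methods do not turn it into a contrast between arms that uses both values. Three analyses fit the text:

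1. A before-after test within each arm. This does not compare the randomised groups. Four separate P values invite the inference that FiO2 matters because one arm reached significance and another did not.
2. A between-arm test of the after-extubation value alone. This is valid under randomisation, but it leaves the pre-induction value unused.
3. A between-arm test of the raw change. This is also valid, but it fixes the weight on baseline at 1 whatever the correlation.

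A pre-induction value precedes any exposure to the assigned FiO2, so it is a legitimate covariate, and the outcome as worded already requires it. At stake are the clarity and precision of one secondary comparison with at most 22 patients per arm.

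**Working it through.** **The plan's own figure.** Section 12.2 gives power 0.9526 for a one-way ANOVA with 17 per arm, means 30, 34, 50 and 53 and SD 19. A noncentral F calculation (SD of means 9.91, effect size 0.5215) returns 0.9526, and 17/(1 − 0.2) = 21.25 rounds up to 22 per arm, 88 in all. This concerns the primary endpoint. The protocol gives no power or precision figure for the oxygenation index.

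**Inputs.** From the protocol: four equal arms, n = 22 enrolled or 17 evaluable per arm. Assumed: r between 0 and 0.8 for the correlation of pre-induction and after-extubation values, and equal SDs at both times.

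**Formulas.** Variance relative to a test of the after-extubation value alone:

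- after-extubation value alone: 1
- raw change: 2(1 − r)
- ANCOVA: (1 − r²) × [1 + 1/(4n − 6)], where the bracket allows for chance baseline imbalance; one error df is lost

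At n = 22 the bracket is 1 + 1/82 = 1.012.

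| r | ANCOVA | Raw change | ANCOVA saving vs after value alone | ANCOVA saving vs change |
|---|---|---|---|---|
| 0 | 1.012 | 2.00 | −1% | 49% |
| 0.3 | 0.91 × 1.012 = 0.921 | 1.40 | 8% | 34% |
| 0.5 | 0.75 × 1.012 = 0.759 | 1.00 | 24% | 24% |
| 0.7 | 0.51 × 1.012 = 0.516 | 0.60 | 48% | 14% |

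**Break-even.** ANCOVA beats the after-extubation value alone when (1 − r²) × 1.012 < 1, that is, for r above about 0.11. At 17 per arm the bracket is 1 + 1/62 = 1.016 and the threshold about 0.13.

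**Detectable pairwise difference** (80% power, two-sided 5%, no multiplicity correction, pooled error), in SD units:

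| n per arm | r | After value alone | Raw change | ANCOVA |
|---|---|---|---|---|
| 22 | 0.3 | 0.855 | 1.011 | 0.820 |
| 22 | 0.5 | 0.855 | 0.855 | 0.745 |
| 22 | 0.7 | 0.855 | 0.662 | 0.614 |
| 17 | 0.3 | 0.976 | 1.154 | 0.938 |
| 17 | 0.5 | 0.976 | 0.976 | 0.852 |
| 17 | 0.7 | 0.976 | 0.756 | 0.703 |

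**On a mmHg scale.** With an assumed SD of 80 mmHg and 22 per arm, the 95% CI half-width for a pairwise difference is t(0.975, 84) × 80 × √(2/22) = 48.0 mmHg. Multiplying by √(1 − r²) gives 45.8, 41.5 and 34.3 mmHg at r = 0.3, 0.5 and 0.7, before the 1% variance allowance.

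**The hazard of the within-arm reading.** Suppose the index changes by the same 0.5 SD in every arm, so FiO2 has no effect on it, and r = 0.5. The SD of the change is then √(2 × 0.5) = 1 SD. With 22 per arm each paired t-test has power 0.609. The chance that some arms are significant and others not is 1 − 0.609⁴ − 0.391⁴ = 0.84.

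**The case against.** Covariate adjustment of a secondary outcome is often left to a statistical analysis plan, and one may exist. Section 12.1 lists tests by data type and assigns none to the oxygenation index by name. That limits the weight of the point. But the protocol does fix both the form of the outcome and a list of methods, and the two do not fit together well.

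A reader might infer that the protocol plans separate before-after tests in each arm. It does not say so. Objective 3.2 links the outcome to the FiO2 levels, so a between-arm question is intended, and the within-arm test is one reading of a short label.

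A reader might also infer that only the t-test and Mann-Whitney U test are available. Section 12.1 names one-way ANOVA for repeated measurements, and count data there may be a slip for measurement data. That clause still supplies no covariate, and a one-way ANOVA across time points would ignore the within-patient correlation.

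Nor does the text support saying that the baseline is already collected or that adjustment is free. T0 is undefined and T5 precedes extubation, so the before/after outcome requires measurements that the schedule does not clearly contain. The gain depends on an unknown r, and the narrow eligibility (ASA I–II, BMI 18–25, the listed pulmonary diseases excluded) could keep r low. At r = 0.3 the gain is small.

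Finally, an unadjusted between-arm test of the after-extubation value is not wrong. It is unbiased under randomisation and gives up only efficiency.

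**Conclusion.** The point holds as a recommended improvement to a secondary outcome. None of the listed methods uses the pre-induction index as a covariate, and the wording leaves open a reading that would bypass the randomised comparison. Compared with testing the after-extubation value alone at 22 per arm, four-arm ANCOVA lowers variance by about 8% to 48% over assumed r of 0.3 to 0.7. It gains nothing below about r = 0.11, and the loss at r = 0 is about 1%. It is more precise than a raw change score at every r examined. These figures assume equal SDs at the two times and rest on no correlation from the protocol. The mismatch between the two-point outcome and the T0–T5 schedule is certain from the text and has to be settled before any of these analyses can be run. The primary analysis and the sample size are not affected.

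**What to change.** - **Section 12.1.** State that the after-extubation oxygenation index is compared across the four arms by ANCOVA, with arm as factor and the pre-induction index as covariate. Give an omnibus test of arm, then multiplicity-controlled pairwise adjusted differences with 95% confidence intervals. A two-sample test does not by itself answer a four-arm question. State that within-arm before-after tests are not evidence of an FiO2 effect.
- **Outcome wording (Summary and objective 3.2).** Name it as the after-extubation oxygenation index compared between arms, adjusted for the pre-induction value.
- **Section 8.** Define T0 as the pre-induction measurement and add the after-extubation measurement. Reconcile this with the T0–T5 wording in the Summary's efficacy row and section 7, and say what role the intraoperative values have.

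**Cost.** A few sentences of text, one error degree of freedom and about 1% of variance. No extra patients are needed, and no measurement beyond the two that the outcome as worded already requires. If practice follows the T0–T5 list alone, the after-extubation measurement must be added whichever analysis is chosen.
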